#### Quantification of serum vitamin D level

Serum vitamin D level was measured using LIAISON 25OH vitamin D Total assay (DiaSorin Inc, USA) based on an automated chemiluminescent immunoassay (CLIA) technology. Serum vitamin D concentration <20 ng/ml was defined as deficiency, <30 and  $\ge$  20 ng/ml as insufficiency, whereas concentrations  $\ge$ 30 ng/ml were considered as sufficiency.

# Quantification of HBV DNA and HBsAg levels

Serum HBV DNA level was quantified using Roche COBAS AmpliPrep/COBAS TaqMan HBV Test (Roche Molecular Systems, Inc, USA). The lower limit of quantification was 20 IU/ml. Serum qHBsAg level was assayed using the Architect HBsAg QT (Abbott Laboratories) according to the manufacturer's instruction. The detection range is from 0.05 to 250 IU/ml. If the qHBsAg level was found to be higher than 250 IU/ml, the samples were 1:100 or 1:1000 diluted to obtain a reading within the range of the calibration curve.

#### **Ethical considerations**

The study was performed in accordance with the principles of the 1975 Declaration of Helsinki and approved by the Ethical Committee of Taipei Tzu Chi Hospital, Buddhist Tzu Chi Medical Foundation. Each participant provided written informed consent at the time of enrollment. The register number of clinical trial is NCT 03068767.

Title: The causal relationship between serum vitamin D level

and hepatitis B virus replication in patients with chronic

hepatitis B virus infection

NCT 03068767

Date of document: 1, June 2017

IRB approval letter (as attached)

Statistical Analyses Plan

Statistical analysis was performed using SPSS version 16.0 (SPSS Inc. Chicago, IL).

Data were analyzed by chi-square test and student's t test. The correlation among

serum vitamin D and FIB-4 was analyzed using Pearson's correlation analysis. The

significance in all of the tests was two-tailed and a p value of less than 0.05 was

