#### **Materials and Methods**

#### Patients and study design

This was a randomized controlled trial. The sample size was determined using two samples t-test power calculation. The 1 log increase of serum HBV DNA level was defined as a significant difference between two samples. Effect size (Cohen'd=0.39) was obtained using two parameters including difference and standard deviation. The power and a significant level were set as 0.8 and 0.05, respectively. The sample size was calculated out as 82 in each group. The ratio of exclusion was estimated as 20 %. Therefore, the sample size was set as 196 in this clinical trial. In our clinical experience, the majority of vitamin D deficiency patients can achieve adequate serum vitamin D levels after two months vitamin D supplement. Furthermore, the liver dysfunction due to hepatitis flare or cirrhosis could be a confounding factor for the low serum vitamin D levels in HBV-infected patients. According to the above consideration, our study was designed to enroll 196 non-cirrhotic, HBV-infected patients with normal or minimally elevated serum ALT levels. Thus, chronic HBV patients receiving regular 6-month surveillance and without current antiviral treatment in the outpatient clinic of Taipei Tzu Chi Hospital were invited to join the study from

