August 2017 to September 2018. All had positive hepatitis B surface antigen (HBsAg) for more than 6 months. Those with positive anti-hepatitis C virus (HCV) antibody, alcoholic liver disease, other known causes of chronic hepatitis or hepatocellular carcinoma were excluded. Cirrhosis was diagnosed based on histological findings or ultrasonographic evidence of nodular liver surface with coarse echotexture and splenomegaly. After obtaining written informed consent, levels of serum vitamin D, HBV DNA and quantitative HBsAg (qHBsAg) levels were measured. Those who had HBsAg loss, undetectable HBV DNA and adequate vitamin D level (≥30 ng/mL) were excluded. The eligible subjects were randomized into two groups by using the computer random distribution. Patients in the vitamin D group received vitamin D supplement (D3, 2000 IU/day; Metagenics, Aliso Viejo, CA 92656) for 2 months and untreated patients were used as the control group. Levels of vitamin D, HBV DNA and qHBsAg before and after 2 months of treatment or follow-up were compared between these two groups. The primary endpoint was to identify any difference between two groups. Patients lost to follow-up or poor drug compliance (vitamin D intake amount < 80%) were excluded for per-protocol analysis. Both intention-to-treat and per-protocol analyses were conducted.

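### The SAP tests the viral outcomes with an unadjusted t-test although baseline values are measured; ANCOVA on log10 values is at least as efficient and needs no new data

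*SAP*

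**What the plan says.** The SAP (Statistical Analyses Plan) states "Data were analyzed by chi-square test and student's t test", then a Pearson correlation of vitamin D with FIB-4, then two-tailed testing at 0.05. The extracted text stops partway through that last sentence, so only the visible part can be judged. In it, Student's t is the only group test for a continuous outcome. No covariate or regression model is named.

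The protocol (Materials and Methods, Patients and study design) gives the rest:

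- After consent and before randomisation, "levels of serum vitamin D, HBV DNA and quantitative HBsAg (qHBsAg) levels were measured".
- For the comparison: "Levels of vitamin D, HBV DNA and qHBsAg before and after 2 months of treatment or follow-up were compared between these two groups". This fits a test of 2-month levels and a test of changes equally well.
- For sizing: "The sample size was determined using two samples t-test power calculation" and "The 1 log increase of serum HBV DNA level was defined as a significant difference between two samples". This implies a log scale for HBV DNA, but the SAP does not repeat it. No scale is given for qHBsAg.

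On the assays (Quantification of HBV DNA and HBsAg levels), the protocol states for HBV DNA "The lower limit of quantification was 20 IU/ml" and for qHBsAg "The detection range is from 0.05 to 250 IU/ml".

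**The concern.** Each patient's baseline viral load is known before allocation and probably predicts the 2-month value. An unadjusted test of the 2-month level ignores that information. A test of the change uses it, but with the coefficient fixed at 1, which adds noise when the true slope is below 1. ANCOVA estimates the slope.

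What is at stake is power and precision. Randomisation makes either t-test valid, and the t-test agrees with the method used for sizing. Because the tested variable is unstated, the analyst would also have to choose between level and change, and which of the two is better depends on a correlation the plan does not give.

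**Working it through.** **Inputs from the documents.** 82 per group, d = 0.39, a difference of 1 log, power 0.8 and alpha 0.05 (Protocol, Patients and study design); two-tailed tests (SAP). The implied SD is 1/0.39 = 2.56 log10. The protocol does not say whether this is the SD of the level or of the change.

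**Assumed, not in the documents.** Baseline-to-2-month correlation ρ of 0.3 to 0.9 and, for the power figures only, equal variances at the two times.

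**The plan's own figure.** With d = 0.39 and 80% power, a one-sided 0.05 t-test needs 81.98, so 82 per group, which reproduces the plan. A two-sided test needs 104.2, so 105. At 82 per group, two-sided power is 69.9%. The sidedness mismatch is a separate sizing point; 69.9% is used here only as the reference value.

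**Ordering of the three analyses.** Let k = baseline SD / 2-month SD. Relative to the variance of the 2-month level:

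- level t-test: 1
- change t-test: 1 + k² − 2ρk = (1 − ρ²) + (k − ρ)²
- ANCOVA: 1 − ρ²

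ANCOVA's factor is never above the other two, whatever k is. It ties with the level test at ρ = 0 and with the change test at k = ρ. Equal variances are not needed for this. The extra degree of freedom costs about 0.6% in variance at 82 per group.

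**Power at 82 per group** (noncentral t, two-sided 0.05, noncentrality = effective d × √(82/2), 162 df for the t-tests and 161 for ANCOVA).

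*If d = 0.39 refers to the level*, the effective d is 0.39 (level), 0.39/√(2(1−ρ)) (change) and 0.39/√(1−ρ²) (ANCOVA). At ρ = 0.5 the ANCOVA value is 0.39/√0.75 = 0.450.

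| ρ | Level t | Change t | ANCOVA | Gain over better t-test |
|---|---|---|---|---|
| 0.3 | 69.9% | 55.5% | 74.0% | 4.1 |
| 0.5 | 69.9% | 69.9% | 81.8% | 11.9 |
| 0.7 | 69.9% | 89.3% | 93.5% | 4.2 |
| 0.8 | 69.9% | 97.5% | 98.5% | 1.0 |
| 0.9 | 69.9% | 100.0% | 100.0% | 0.0 |

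*If d = 0.39 refers to the change*, the effective d is 0.39·√(2(1−ρ)) (level), 0.39 (change) and 0.39/√((1+ρ)/2) (ANCOVA). The implied SD of the level is 2.56/√(2(1−ρ)).

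| ρ | Level t | Change t | ANCOVA | Gain over better t-test | Implied level SD (log10) |
|---|---|---|---|---|---|
| 0.3 | 83.6% | 69.9% | 86.8% | 3.2 | 2.17 |
| 0.5 | 69.9% | 69.9% | 81.8% | 11.9 | 2.56 |
| 0.7 | 48.5% | 69.9% | 76.8% | 6.9 | 3.31 |
| 0.8 | 34.8% | 69.9% | 74.4% | 4.5 | 4.05 |
| 0.9 | 19.9% | 69.9% | 72.1% | 2.2 | 5.73 |

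Level SDs of 3.3 log10 and above are implausible, so the last three rows of this second table deserve little weight. At ρ = 0 and 0.1 the gain is 0.0 and 0.4 points (d on level) or 0.0 and 0.3 (d on change).

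**Does the assay limit change this?** A simulation with d on the level set HBV DNA below log10(20) = 1.30 to 1.0 at both times. It assumed means of 3, 4 or 5 log10, the five correlations, effects in either direction, and below-limit baselines either eligible (7–25% of patients) or excluded. That makes 3 × 5 × 2 × 2 = 60 cells of 20,000 replicates. ANCOVA gained 0.0 to 11.3 points over the better t-test and was never below it. Its type I error was 4.8–5.0%. Substituting log10(19) instead of log10(10) moved ANCOVA power by at most about 1 point.

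**The case against.** The strongest reply is that nothing is broken. The t-test is valid, sizing and analysis use the same method, and the benefit depends on a correlation nobody has stated. The trial re-measures untreated, non-cirrhotic patients with little or no ALT elevation after only 2 months. If viral load is stable in such patients, the correlation is high and a t-test on the change would capture nearly all the gain: 97.5% against 98.5% at ρ = 0.8 with d on the level. On this view the real defect is the unstated variable and scale, and naming the change in log10 would be a simpler cure.

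Much of this stands. The 12 points are a best case, and the large gaps against the weaker t-test (for example 69.9% for level against 97.5% for change at ρ = 0.8) are not credited to ANCOVA, because naming the better t-test would recover most of them. But that naming requires the correlation to be guessed in advance, with the change test losing below 0.5 and the level test losing above it. ANCOVA needs no such guess, and at worst it costs one degree of freedom.

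Three smaller points also stand. The change is not wholly free, since it needs a scale and a below-limit rule, though a log-scale t-test would need these too. The power figures concern HBV DNA only, because the documents give no effect size or SD for qHBsAg. For qHBsAg a below-limit rule will rarely bite at baseline, because patients must be HBsAg-positive.

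**Conclusion.** The concern holds as an efficiency improvement that should be made, not as an error that threatens validity. The ordering (ANCOVA at least as efficient as either t-test) is a large-sample result, holds for any SD ratio, and is subject only to the loss of one degree of freedom. The size of the gain is uncertain. At 82 per group and d = 0.39 it is about 12 points of power over the better t-test at an assumed correlation of 0.5, about 3 to 4 points at 0.3, and 0 to 2 points at 0.9, under equal variances. At 0.5, power rises from about 70% to about 82% under either reading of d. The judgement rests on the visible SAP text.

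**What to change.** Replace the t-test for the viral outcomes in the SAP with text such as:

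> Log10 HBV DNA at 2 months and, separately, log10 qHBsAg at 2 months will be compared between the randomised groups by ANCOVA with the baseline log10 value of the same marker as covariate. The adjusted difference and its 95% CI will be reported. The model will be fitted in both the intention-to-treat and the per-protocol analysis. Baseline and follow-up values below the assay limit (HBV DNA 20 IU/mL, qHBsAg 0.05 IU/mL) will be set to half the limit (10 and 0.025 IU/mL), with a sensitivity analysis using another prespecified value.

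Half the limit is one reasonable choice and matches the HBV DNA value in the simulation; what matters is that a value is fixed beforehand. The rule must cover baseline as well as follow-up. The protocol's exclusion list reads "Those who had HBsAg loss, undetectable HBV DNA and adequate vitamin D level", while 20 IU/mL is a limit of quantification, so a patient with detectable but unquantifiable HBV DNA may be eligible.

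The t-test may be kept as a supporting analysis, on a stated variable and scale. Which viral marker is primary is a separate matter.

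Cost: a few SAP sentences, one degree of freedom and one sensitivity analysis. No extra patients, visits or assays are needed, because both measurements are already planned.

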# Laboratory testing

Serum aspartate aminotransferase (AST) and alanine aminotransferase (ALT) were measured using routine automated methods (Dimension Flex®reagent cartridge, USA; SIEMENS, Dimension, NY, USA). The upper limit of normal of ALT was 63 U/L in men and 59 U/L in women. The HBeAg and Anti-HCV were assayed using Abbott ARCHITECT, Wiesbaden, Germany. The Fibrosis 4 index (FIB-4) was calculated base on the formula: FIB-4=Age (years)×AST (U/L)/[PLT(109/L)×ALT1/2(U/L)]. Based on our previous study, FIB-4 >= 0.87 was defined as the presence of significant fibrosis (>=F2).

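### The planned vitamin D–FIB-4 correlation is not adjusted for age, although age is a multiplier in FIB-4, so an age–vitamin D link alone could make it significant (a minor, secondary point)

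*SAP*

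**What the plan says.** The SAP (Statistical Analyses Plan) states that the correlation among "serum vitamin D and FIB-4 was analyzed using Pearson's correlation analysis". The only other methods it names are in the sentence "Data were analyzed by chi-square test and student's t test". It adds that "significance in all of the tests was two-tailed", with a 0.05 threshold. Neither document names a covariate, a partial correlation, a regression model, a transformation or a rank method. The supplied SAP text does not say whether the vitamin D value is the one before or after the two months.

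The protocol (Laboratory testing) computes FIB-4 as age × AST / (platelets × √ALT) and takes a value of 0.87 or more to mean fibrosis of stage F2 or higher. Under Patients and study design it excludes people with vitamin D of 30 ng/mL or more, and limits entry to patients without cirrhosis whose ALT is normal or only slightly raised.

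**The concern.** Age raises FIB-4 in direct proportion even if every liver marker stays fixed. For illustration, assume AST 25, ALT 27 and platelets 210. Then FIB-4 = age × 25 / (210 × √27) = 0.0229 × age. The 0.87 cut-off is reached at about age 38 (0.87 / 0.0229), and the score is 1.15 at age 50, with identical laboratory values.

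Any relation between age and vitamin D therefore passes into the planned coefficient with no fibrosis link. Because the protocol treats FIB-4 as a fibrosis marker, a significant result invites the statement that vitamin D is related to liver fibrosis. At stake is that one secondary claim and the size reported for it.

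**Working it through.** **The plan's own figure.** The documents give none for this correlation. The sample sizes used here are the protocol's total of 196 and, as the smaller case, 2 × 82 = 164.

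**How small a correlation is significant.** With r = t / √(t² + n − 2), two-sided 0.05:
- n = 196: t = 1.972, r = 1.972 / √(3.890 + 194) = 0.140
- n = 164: t = 1.975, r = 1.975 / √(3.900 + 162) = 0.153

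**How much correlation age alone creates.** Write FIB-4 = age × L, where L = AST / (platelets × √ALT). If L is independent of age and vitamin D, the covariance of vitamin D with FIB-4 is the mean of L times the covariance of vitamin D with age. Hence

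r(vitamin D, FIB-4) = r(vitamin D, age) × r(age, FIB-4).

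**Base-case assumptions (none is in the documents).** Age 50, SD 12; AST, ALT and platelets log-normal with medians 25, 26 and 200 and log-SDs 0.25, 0.40 and 0.25; AST and ALT correlated at 0.7 on the log scale; vitamin D mean 24, SD 8, linked to age only. These give r(age, FIB-4) = 0.59 and FIB-4 skewness of about 1.0.

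**Hand check at n = 196.** With Fisher's z and √193 = 13.89, the rejection rate is about Φ(z − 1.96) + Φ(−z − 1.96):
- age link 0.1: r = 0.059, z = 0.82, rate 13%
- age link 0.2: r = 0.118, z = 1.65, rate 38%
- age link 0.3: r = 0.177, z = 2.49, rate 70%

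**Simulation, 3,000 runs per setting.** The share significant in the base case, with vitamin D unrelated to L:

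| Age–vitamin D r | Pearson, n = 196 | Spearman, n = 196 | Pearson, n = 196, vitamin D < 30 | Pearson, n = 164 | Pearson, n = 164, vitamin D < 30 |
|---|---|---|---|---|---|
| 0 | 5.3% | 5.2% | 5.1% | 5.1% | 4.6% |
| 0.1 | 12.7% | 12.5% | 8.9% | 10.8% | 8.2% |
| 0.2 | 38.8% | 38.7% | 24.3% | 30.7% | 20.0% |
| 0.3 | 71.0% | 71.2% | 47.9% | 63.0% | 41.9% |

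In the restricted columns, r is the value before people with 30 ng/mL or more are removed. The restriction weakens it: for 0.2, the mean correlation with FIB-4 falls from 0.119 to 0.090.

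After adjustment for age, on raw or log FIB-4, the rate was about 4–6% in every setting.

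**Other assumptions, n = 196.**
- A further simulation gave 11%, 28% and 54% for age links of 0.1, 0.2 and 0.3, and 9%, 20% and 41% with vitamin D below 30. By the formula above, its unrestricted rates correspond to r(age, FIB-4) near 0.49 (0.2 × 0.49 = 0.098, z = 1.37, rate 28%). With the base case, this gives the ranges 9–13%, 20–39% and 41–71%.
- Varying the age and laboratory spreads so that r(age, FIB-4) runs from 0.31 to 0.73, with the full vitamin D range, gives 14–52% at an age link of 0.2 and 26–87% at 0.3.

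**Skewness on its own.** With no age link, Pearson rejected in 4.5–5.3% of runs across all settings, including one with FIB-4 skewness of about 2.2.

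**The case against.** The strongest reply is that the harm depends on a link the documents do not report. They give no age distribution, no age–vitamin D correlation and no laboratory spreads. That stands: with no link the planned test behaves properly, and the entry limit of 30 ng/mL weakens any link there is.

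Second, a Pearson test asks only whether vitamin D and FIB-4 are linearly associated. In these scenarios they are, so rejection is correct for that hypothesis. This also stands; the error lies in reading the result as fibrosis. The protocol's cut-off makes that reading natural, so the risk is real.

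Third, age is part of the score by design, so adjusting for it removes some of the marker. That is a fair cost, met by reporting both values.

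Three stronger readings are tempting, and the documents do not support them.
- A reader might infer that FIB-4 is skewed and that Pearson is invalid for that reason. No FIB-4 distribution is given, the eligibility limits restrict extreme values, and skewness alone did not raise the error rate. A change to Spearman without age adjustment leaves the problem as it was.
- A reader might take the protocol's remark that "the liver dysfunction due to hepatitis flare or cirrhosis could be a confounding factor for the low serum vitamin D levels in HBV-infected patients" as a statement about this correlation. In context it justifies the choice of patients and does not mention FIB-4.
- A reader might conclude that the trial's main result is compromised. The stated aim concerns HBV DNA and qHBsAg, compared between randomised groups, and this correlation plays no part in that comparison.

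**Conclusion.** The point holds as a minor one. The planned correlation is unadjusted and age is built into FIB-4, so an age–vitamin D link would produce an apparent fibrosis association where none exists. At n = 196, links of 0.1, 0.2 and 0.3 give roughly 9–13%, 20–39% and 41–71% significant results, against about 5% with age adjustment. These figures rest on assumed age and laboratory spreads, on AST, ALT and platelets being unrelated to age and vitamin D, and on an assumed age link. They show what could happen and do not predict that it will. The effect is confined to one secondary observational analysis.

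**What to change.** Replace the SAP sentence with one that relates baseline vitamin D to baseline FIB-4 adjusted for age. Either a partial correlation or a linear regression of log FIB-4 on vitamin D with age as covariate would do. On the log scale, log age is the natural form, since log FIB-4 = log age + log AST − log platelets − ½ log ALT. Report the unadjusted correlation alongside and label the analysis exploratory. Using baseline values keeps the randomised supplement out of the relation. A rank-based version is optional, provided it is also adjusted for age.

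The cost is one sentence and no new data, because age is already needed to compute FIB-4. The downside to state in the report is that the adjusted result describes only the age-independent part of FIB-4.
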